During the dose-escalation phase, study treatment will be administered as outlined in [Table 1](#). Patients who achieve remission (CR, CRi, CRp, or CRh) after up to 2 induction cycles will receive chemotherapy consolidation treatment up to 4 cycles or allo-HSCT consolidation at the investigator's discretion. Patients who achieved a confirmed remission at the end of chemotherapy consolidation or allo-HSCT or who underwent allo-HSCT in MLFS after induction (see definition of MLFS in [Appendix 19](#)) will receive maintenance treatment for 12 cycles (see [Table 1](#)). In cases where the patient receives allo-HSCT consolidation, maintenance should start within 90 days of the transplant and a full pre-transplant hematologic response assessment must be provided if the transplant is performed more than 4 weeks after end of induction. Patients receiving chemotherapy consolidation should start maintenance right after completion of the consolidation. On the basis of safety, tolerability, and clinical benefit and after consultation with the Medical Monitor, patients may be allowed to continue maintenance at the same dose beyond 12 cycles. All patients will be followed for disease progression and survival. The dose for idasanutlin in consolidation will be determined by the Sponsor upon review of all available safety, PK, pharmacodynamic, and efficacy data. The dose for consolidation will not exceed the dose the patient received during induction.

After the last patient in each cohort has completed the DLT assessment window (first induction cycle), the Sponsor will evaluate the next dose recommended according to the mCRM (see Section [3.1.2.3](#)) and determine doses for the subsequent cohort(s), taking into account relevant demographic, adverse event, laboratory, dose administration, and PK (if available) data. At each dose-escalation step, the dose may be escalated or de-escalated, or an additional cohort at the same dose level may be enrolled.

On the basis of review of real-time safety data from this study and all available data from other studies in the program, dose escalation may be halted or modified by the Sponsor as deemed appropriate.

Although the DLT assessment window is defined as the first induction cycle, cumulative toxicities occurring beyond the first cycle may be considered when determining the MTD for idasanutlin. At the end of the dose-escalation phase, the idasanutlin RP2D in combination with cytarabine and daunorubicin will be decided.

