3.1.2.3 Use of mCRM for Dose and MTD Determination

The dose escalation will employ a mCRM with overdose control design in order to define the MTD and/or the recommended dose for subsequent cohorts.

The design is based on the primary safety variable, that is, the occurrence of a DLT. The MTD is defined as the dose that maximizes the probability of a DLT being in the targeted toxicity interval of 25%–35%, subject to the probability of the DLT being in the

excessive toxicity interval of 35%–100% being <35%. Simulations of the designs under various scenarios of true toxicity are presented in [Appendix 18](#).

Patients within a phase will be enrolled in cohorts of at least 3 patients each, which, if required, can be expanded with additional patients. Each patient will be observed over 1 cycle of treatment for DLT assessment. After the last patient in each cohort has completed the first cycle of the observation period, the next dose recommended by the mCRM design will be evaluated and that analysis will support the dose decision for the subsequent cohort. At each dose-escalation step, the dose can be escalated, the dose can be de-escalated, or an additional cohort at the same dose level can be enrolled. The idasanutlin starting dose will be 200 mg QD on Days 1–5, and maximum allowable increments for the highest dose already tested will not exceed 150 mg, with a minimum increment of 50 mg. In addition, the dose of idasanutlin will not be escalated above 800 mg QD. The selection of the next dose will be subject to clinical judgment and mandated safety constraints that limit the size of the dose increments. Clinical judgment will always override mCRM recommendations in the dose-selection process.

Dose escalation will stop when the maximum allowed sample size, approximately 15 evaluable patients, has been reached or if there is enough confidence in the prediction of the MTD (e.g., at least 6 patients have been recruited at the MTD dose and there is a >40% probability of having a DLT rate of 25%–35%).

The dose–toxicity relationship is described by a two-parameter logistic regression model:

$$\text{logit}(p(d_i^*)) = \alpha_1 + \beta_1 \log(d_i^*)$$

In this model, α_1 and β_1 are model parameters and $p(d_i^*)$ is the probability of experiencing a DLT at a dose d_i^* , where $d_i^* = \frac{d_i}{d^R}$ being the normalized dose using the reference dose $d^R=300$ mg.

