In order to define the prior distributions (priors) for the parameters of the model, the Sponsor's clinical team completed Bayesian prior elicitation to reach a consensus on the following questions, based on expert knowledge and previous idasanutlin data (e.g., Studies NP27872 and BH29812):

- What is the (low) probability that the DLT rate for the lowest-tested dose (200 mg) is above a threshold of 30%?
- What is the (low) probability that the DLT rate for the highest potentially tested dose (800 mg) is below a threshold of 30%?

[figure not shown]
These probabilities reflecting the prior knowledge of dose toxicity were chosen by the team to be 40% and 25%, respectively, for the first and second questions. Of note, a lower or a higher probability would reflect respectively more or less prior knowledge that is borrowed by the model.

As a consequence of this choice, the following prior was defined:

$$\begin{bmatrix} \alpha_1 \\ \beta_1 \end{bmatrix} \sim N \left[\begin{pmatrix} -0.797 \\ 0.995 \end{pmatrix}, \begin{pmatrix} 1.699 & 0.280 \\ 0.280 & 1.076 \end{pmatrix} \right]$$

A visual representation of the prior is shown in [Figure 4](#).

Figure 4 Selected Prior Distribution with 95% Credible Interval

DLT = dose-limiting toxicity.

Consider the various hypothetical trial realizations. If 3 patients are given the starting dose of 200 mg and none develop a DLT, then the next mCRM dose recommendation is 350 mg. Afterward the mCRM recommendations are 450 and 600 mg if the next cohorts of 3 patients also have no DLT observed each time.

If DLTs are observed, the next recommended dose is (almost) equal to or lower than the current dose. Specifically, if the first cohort is at 200 mg QD with 3 patients when one DLT is observed, then the dose recommended for the second cohort is again 200 mg QD. If the first DLTs are observed in the second cohort of 3 patients at 300 mg QD and none in the first cohort of 200 mg QD, the dose for the third cohort is recommended as 300 mg QD. When two or three DLTs are observed in a cohort, a dose de-escalation is always recommended by the model (even if no DLTs were observed in previous cohorts).

A summary of dose recommendations among same principle is provided in [Table 2](#). Of note, these recommendations are subject to the constraint that the dose increase in the subsequent cohort cannot exceed a 50% increment of the previous cohort dose.

Table 2 Hypothetical Trial Realizations (Cohort Size=3)

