Appendix 18: mCRM Simulations (cont.)

The model (1) thus can be rewritten as (2):

$$\ln\left(\frac{p(d_j)}{1-p(d_j)}\right) = \alpha + \beta x_j \quad (2)$$

where α and β are the parameters to be estimated and assumed to follow a bivariate normal distribution.

Model Prior

A minimally informative bivariate normal prior for the parameters of the DLT-dose response curve (α, β) is constructed in order to have a weak impact to the final MTD determination (B, M, and T 2008).

[figure not shown]
The parameters of the minimally informative prior are listed below (3):

$$\begin{aligned} \mu = (\alpha, \beta) &= (-0.797, 0.995) \\ \Sigma &= \begin{pmatrix} \sigma_\alpha^2 & \sigma_{\alpha\beta} \\ \sigma_{\alpha\beta} & \sigma_\beta^2 \end{pmatrix} = \begin{pmatrix} 1.699 & 0.280 \\ 0.280 & 1.076 \end{pmatrix} \end{aligned} \quad (3)$$

where μ and Σ are the parameters of the bivariate normal distribution.

The prior distribution used to determine the dose-escalation decision for this study is shown in [Figure 1](#).

Figure 1 Minimally Informative Prior

Maximum Dose Increments

The maximum dose increments relative to the previous dose level is 150 mg. Only increments that are multiples of 50 mg (e.g. 50 mg, 100 mg or 150 mg) are allowed.

Stopping Rules

The algorithm will recommend ending the dose escalation if any of the following criteria applies:

- Maximum number of patients: the maximum sample size of 15 DLT-evaluable patients has reached **OR**
- Enough information on MTD: at least a minimum of 6 patients evaluated *and* at least 6 patients have been accrued near the MTD dose (where near means differing from the MTD by at most 5%) *and* the posterior probability that the MTD dose lies within the target toxicity interval is above 50% **OR**
- Maximum dose is safe: at least 6 subjects have been observed at the maximum dose or near (differing from the maximum dose by at most 0.05%) *and* it is at least 50% likely that the probability of a DLT for the maximum dose is below 0.2.

Dose Grid

The dose grid that has been used in this design starts from 200 mg and ends at 800 mg, with an increment of 50 mg.

Model Performance Evaluation

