To illustrate how the design will perform, different escalation scenarios are explored and results are tabulated in [Table 1](#). Each row represents four different situations: which dose would the model recommend, after seeing no DLTs in previous cohorts and when 0, 1, 2, or 3 DLTs are observed in the current cohort. The evaluation is based on cohort size=3, “<200” indicates that the model would stop escalating and the trial would be halted.

Table 1 Hypothetical Trial Realizations (Cohort Size=3)

| Dose (mg) at which the First DLTs Were Observed (mg) | Number of DLTs | Recommended Next Dose (mg) |
|--|----------------|----------------------------|
| 200 | 0 | 350 |
| 200 | 1 | 200 |
| 200 | 2 | <200 |
| 200 | 3 | <200 |
| 350 | 0 | 450 |
| 350 | 1 | 300 |
| 350 | 2 | 200 |
| 350 | 3 | <200 |
| 450 | 0 | 600 |
| 450 | 1 | 450 |
| 450 | 2 | 300 |
| 450 | 3 | 200 |

As can be seen from the Table above, in general in presence of no DLTs the model will suggest to escalate close to what the max increment allow, while in presence of one DLT the increment is in general zero. Then, with 2 or 3 DLTs the model always recommends to de-escalate or STOP. Therefore, the results show that the design will adequately adapt the dose in the presence of observed DLTs.

Simulation Study

A simulation study is conducted to evaluate the operating characteristics for the chosen design parameters (priors, reference dose, stopping rule) under various dose-toxicity scenarios. The different scenarios have been selected in order to cover a wide range of dose-toxicity possibilities and to be able to quantify the risk and benefit, should these scenarios actually occur.

Dose–Toxicity Scenarios

[figure not shown]
The different scenarios have been selected in order to cover a wide range of dose-toxicity possibilities and to be able to quantify the risk and benefit, should these scenarios actually occur.

As shown in [Figure 2](#), we explore 6 scenarios. The first 5 represent decreasing levels of toxicity, while the last one considers the toxicity depicted in the prior as true toxicity. Scenario 3 has a steeper dose-toxicity curve meaning that the acceptable dose interval is very narrow. Some scenarios are relatively extreme, but still they will be informative on

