Appendix 18:mCRM Simulations (cont.)**Table 2 Summary of Simulations Results**

| Scenario | Target Dose Interval | Total Number of Patients | Number of Patients Treated Above Target Toxicity | Proportion of DLTs in the Trials | Dose Selected as MTD |
|----------|----------------------|--------------------------|--|----------------------------------|----------------------|
| 1 | 50 - 100 | 3 (3, 9) | 3 (3, 9) | 66.7% (33.3%, 100%) | 0 (0, 0) |
| 2 | 100 - 200 | 6 (3, 15) | 6 (3, 15) | 41.7% (26.7%, 66.7%) | 0 (0, 250) |
| 3 | 200 - 280 | 15 (3, 15) | 3 (0, 12) | 33.3% (20%, 66.7%) | 200 (0, 300) |
| 4 | 350 - 700 | 15 (3, 15) | 0 (0, 0) | 20% (6.7%, 33.3%) | 350 (0, 650) |
| 5 | 500 - 1000 | 15 (6, 15) | 0 (0, 0) | 13.3% (6.7%, 33.3%) | 450 (0, 750) |
| 6 | 166 - 359 | 15 (3, 15) | 0 (0, 6) | 33.3% (20%, 66.7%) | 200 (0, 400) |

From these simulations, it can be seen that the design is able to provide a reliable estimate of the MTD: usually, the median of the doses selected as MTD is within or slightly below the target toxicity dose range (at the lower end of the range), which means that the design is relatively conservative.

For dose-toxicity curves corresponding to most toxic scenarios (e.g. scenarios 1, 2) the median selected dose is 0, indicating that no MTD within the tested dose range can be found most of the time. In these cases, the required number of treated patients is far less than 15 evaluable patients, meaning that the design tends to recommend stopping dose escalation, avoiding therefore unnecessary exposure to toxic doses

In addition, we see that the number of patients treated over the dose toxicity interval is quite limited, with the exception of the first two scenarios where all doses were too toxic (all patients being treated at or above the target toxicity).

The good performances of the algorithm are also confirmed by the median proportion of DLTs observed in the simulations, which is always $\leq 1/3$ (except for toxic scenarios 1 and 2).

Finally, in terms of sample sizes, the median number of patients required to give a MTD recommendation is usually 15 patients across all scenarios. In case of too high toxicity, the required number is, as outlined above, lower.

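### Table 2 of Section 3.1.2.3 permits another cohort at 200 mg where the plan's own overdose limit forbids it, and the halt that Appendix 18 applies there is in neither stopping list

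*Combined protocol and SAP*

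**What the plan says.** Section 3.1.2.3 describes an mCRM with overdose control. A recommended dose must have a posterior probability below 35% that its DLT rate exceeds 35%. On ending escalation the section says: "Dose escalation will stop when the maximum allowed sample size, approximately 15 evaluable patients, has been reached or if there is enough confidence" in the predicted MTD, for example at least 6 patients at that dose and more than 40% probability of a DLT rate in the target interval. Appendix 18, Stopping Rules, opens with "The algorithm will recommend ending the dose escalation if any of the following criteria applies" and lists three: 15 evaluable patients, enough information on the MTD (at least 6 patients), or a safe maximum dose (at least 6 patients).

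The options at each step are in Section 3.1.2.2: "At each dose-escalation step, the dose may be escalated or de-escalated, or an additional cohort at the same dose level may be enrolled". Section 3.1.2.3 repeats them.

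On toxic cohorts, Section 3.1.2.3 says: "When two or three DLTs are observed in a cohort, a dose de-escalation is always recommended by the model". The matching sentence in Appendix 18 is "with 2 or 3 DLTs the model always recommends to de-escalate or STOP".

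The two versions of the hypothetical-realizations table differ in three rows (2/3 at 200 mg, 3/3 at 200 mg, 3/3 at 350 mg). Table 2 of Section 3.1.2.3 prints ≤200 without defining it. Appendix 18 Table 1 prints <200 and explains that this "indicates that the model would stop escalating and the trial would be halted".

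On the floor, the prior-elicitation question in Section 3.1.2.3 asks for the probability that "the DLT rate for the lowest-tested dose (200 mg) is above a threshold of 30"%, and the Appendix 18 dose grid starts at 200 mg.

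**The concern.** Because 200 mg is the lowest dose on the grid, the equals sign in ≤200 can only mean another cohort at 200 mg. In the two rows that start from 200 mg, the instruction to de-escalate has no defined dose to go to. Section 3.1.2.3 leaves out the stop that Appendix 18 includes.

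This is the design's model-based protection against a starting dose that is too toxic, in a regimen that adds idasanutlin to 7+3 with acknowledged overlapping toxicity. The reported operating characteristics depend on it. For the two most toxic scenarios Appendix 18 states: "In these cases, the required number of treated patients is far less than 15 evaluable patients", and it credits the design with sparing patients needless exposure to toxic doses. The listed early-stopping criteria need at least 6 patients, so they cannot produce the 3-patient trials in the simulation summary. Those trials come from a halt that neither list contains.

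A team working from the body of the protocol could enrol a further cohort at 200 mg where the model admits no dose.

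**Working it through.** **Inputs.** Section 3.1.2.3 and Appendix 18 give logit p(d) = α + β ln(d/300), with (α, β) bivariate normal, mean (−0.797, 0.995), variances 1.699 and 1.076, covariance 0.280. The overdose limit is P(p > 0.35) < 0.35. The grid runs from 200 to 800 mg in steps of 50 mg. Cohorts are of 3, with no DLTs in earlier cohorts, as in the tables. The posterior was integrated numerically on a grid of (α, β).

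**The plan's own figures first.** The prior gives P(p(200) > 0.30) = 0.39 and P(p(800) < 0.30) = 0.29, against elicited values of 40% and 25%. With the Appendix 18 target of 20%–35%, 9 of the 12 table rows reproduce, including all three in dispute. The other three differ by 50 mg (500 v 450 after 0/3 at 350 mg; 350 v 300 and 250 v 200 after 2/3 and 3/3 at 450 mg). The disputed rows depend only on the overdose limit, not on the target interval.

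**Posterior P(p > 0.35) at 200 mg.**

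| Data | Value | Limit 0.35 | Table 2 | Appendix 18 |
|---|---|---|---|---|
| 1/3 at 200 | 0.341 | met | 200 | 200 |
| 2/3 at 200 | 0.691 | exceeded | ≤200 | <200 (halt) |
| 3/3 at 200 | 0.918 | exceeded | ≤200 | <200 (halt) |
| 0/3 at 200, 2/3 at 350 | 0.220 | met | 200 | 200 |
| 0/3 at 200, 3/3 at 350 | 0.431 | exceeded | ≤200 | <200 (halt) |

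In the three exceeded rows every higher grid dose has a larger overdose probability than 200 mg, so no dose is admissible.

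**How often the rows arise: Scenario 6.** This scenario takes the prior curve as the truth. At the prior mean, p = 0.20 falls at 166 mg and p = 0.35 at 359 mg, which is the interval printed in the Appendix 18 simulation summary, so no curve has to be guessed.
- p(200) = expit(−0.797 + 0.995 ln(200/300)) = 0.2314; p(350) = 0.3444.
- P(2 or 3 of 3 at 200 mg) = 3(0.2314²)(0.7686) + 0.2314³ = 0.136.
- P(0/3 at 200 mg, then 3/3 at 350 mg) = 0.7686³ × 0.3444³ = 0.454 × 0.0409 = 0.019.
- Any of the three rows: 0.1359 + 0.0186 = 0.154.

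The first-cohort figure, 13.6%, agrees with the printed 10th percentile of 3 patients. In 5,000 simulated trials, about 43% reached a point with no admissible dose by some path. That falls to 37% if 2/6 at 200 mg (posterior 0.351) is treated as admissible. Appendix 18 itself prints a 10th-percentile selected dose of 0 in all six scenarios.

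**What the halt does: Scenarios 1 and 2.** The scenario figure is not available, so the curves are an assumption: logistic in log dose, passing through 20% and 35% at the ends of the printed target interval. This puts the DLT rate at 200 mg at about 54% in Scenario 1 and 35% in Scenario 2. Settings: 5,000 trials each, cohorts of 3, at most 15 patients, steps of at most 150 mg.

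| Scenario | Printed N | N with halt | Mean N / mean DLTs, halt | Mean N / mean DLTs, 200 mg repeated |
|---|---|---|---|---|
| 1 | 3 (3, 9) | 3 (3, 9) | 5.0 / 2.7 | 15 / 8.1 |
| 2 | 6 (3, 15) | 6 (3, 15) | 8.0 / 3.1 | 15 / 5.6 |

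The printed sizes appear only with the halt, under either the appendix settings (20%–35%, 50%) or the body settings (25%–35%, 40%).

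**The case against.** The best reply is that the halt is already in the plan. The overdose limit governs the dose for later cohorts, so in these rows the model returns no dose, and Appendix 18 says what happens then. Table 2 is illustrative, and the Sponsor reviews the actual model output after each cohort. The prose calling for de-escalation rules out repeating 200 mg in the two rows that start there. The Sponsor may halt at any time, clinical judgment overrides the model, and ≤200 may be a slip for <200, since Table 2 prints a plain 200 elsewhere.

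Much of this stands. The halt can be inferred, and the 15-patient figures assume that nobody intervenes. But inference and discretion are not a stopping rule, whereas the simulated performance assumes an automatic stop. The de-escalation sentence also does not protect the 350 mg row, where 200 mg is itself a de-escalation.

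A second reply is that 150 mg is feasible: a 50 mg tablet exists and maintenance uses 150 mg. The escalation plan does not provide for that dose. It would also fail after 2/3 (0.575) and 3/3 (0.851) at 200 mg, though it would pass after 3/3 at 350 mg (0.237).

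A third concerns the rebuilt curves. They match the printed patient numbers for Scenarios 1 and 2, but the same rebuilding does not match all printed percentiles for Scenarios 4 and 5, so the DLT counts above are approximate.

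**Conclusion.** The concern holds and should be fixed. Three cells of Table 2 admit a dose with an overdose probability of 0.69, 0.92 or 0.43 against a limit of 0.35. The halt that Appendix 18 simulates in those rows is missing from both stopping lists. These values rest only on the printed model, prior and limit.

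The situation is not confined to extreme toxicity: the three rows have a combined probability of 15.4% under Scenario 6, where 200 mg lies inside the Appendix 18 target interval. The larger contrast, about 8.1 v 2.7 mean DLTs in Scenario 1 and 5.6 v 3.1 in Scenario 2, rests on rebuilt curves and on 200 mg being repeated without Sponsor intervention. It is the worst case, not the expected outcome. The simulations themselves are not at fault; the body of the protocol does not match them.

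**What to change.** - Add to the stopping rules in both Section 3.1.2.3 and Appendix 18: stop dose escalation if no dose on the grid has a posterior probability below 35% that its DLT rate exceeds 35%.
- In Table 2 of Section 3.1.2.3, change the three ≤200 cells to <200 (stop).
- In the prose above Table 2, add the words \"or stop\" in substance, so that two or three DLTs lead to de-escalation or a stop, as in Appendix 18.

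The cost is one sentence in two places, two words and three cells. It needs no extra patients and no new simulation, because it writes down what Appendix 18 already describes. If the Sponsor would rather allow doses below 200 mg, those doses must be added to the grid and Appendix 18 re-run.

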| Dose (mg) at Which the First DLTs Were Observed (mg) | Number of DLTs | Recommended Next Dose (mg) |
|--|----------------|----------------------------|
| 200 | 0 | 350 |
| 200 | 1 | 200 |
| 200 | 2 | ≤200 |
| 200 | 3 | ≤200 |
| 350 | 0 | 450 |
| 350 | 1 | 300 |
| 350 | 2 | 200 |
| 350 | 3 | ≤200 |
| 450 | 0 | 600 |
| 450 | 1 | 450 |
| 450 | 2 | 300 |
| 450 | 3 | 200 |

DLT=dose-limiting toxicity.

The operating characteristics of the proposed mCRM were also carefully evaluated through the use of simulations across different scenarios, and the results are reported in [Appendix 18](#). The general conclusion is that the current design provides, with an assumed sample size of approximately 15 evaluable patients, overall good performances in selecting the correct MTD, while at the same time limiting the potential amount of overdose across all scenarios.

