Appendix 17: Prohibited Medications (cont.)

Table 3 Prohibited OATP1B1/3 Substrates

| OATP1B1/3 Substrates ^a |
|-----------------------------------|
| Atorvastatin |
| Atrasentan |
| Bosentan |
| Ezetimibe |
| Fluvastatin |
| Glyburide |
| Irinotecan |
| Olmesartan |
| Pitavastatin |
| Pravastatin |
| Repaglinide |
| Rifampin |
| Rosuvastatin |
| Simvastatin Acid |
| Telmisartan |
| Valsartan |

OATP1B1/3=organic anion-transporting polypeptide 1B1/3.

^a OATP1B1/3 substrates with a half-life shorter than 1 day are allowed except during idasanutlin treatment and for 72 hours after the last dose of idasanutlin.

Appendix 18

Modified Continual Reassessment Method Simulations

Dose Escalation

This appendix provides details of the design that will guide the dose-escalation stage of this study and of its operating characteristics through simulations. All analyses were performed using the R statistical software R version 3.4.4 (2018-03-15) (Team 2017) (see Section 3.1.2.3 for additional information).

Rationale for Model-Based Design

The modified continuous reassessment method (mCRM) design uses a statistical model that actively seeks a dose level close to the maximum tolerated dose (MTD) by using toxicity data from all enrolled evaluable patients to compute a precise dose-toxicity curve. It locates the MTD efficiently and minimizes the number of patients treated at possibly pharmacological inactive dose levels. Such model-based designs have been successfully applied in many Phase I dose-escalation studies (S. P et al. 2004; C, JJ, and LL 2009; B, M, and T 2008). The simulations in this appendix investigate the operating characteristics of the design as implemented for this study.

In this design the MTD is defined as the dose maximizing the posterior probability that the DLT rate, $\pi(MTD) \in [0.2, 0.35]$ while keeping the probability of overdose $P\{p(MTD) > 0.35\} < 0.35$.

Statistical Model

A two-parameter logistic model will be used to fit the dose-toxicity relationship. The probability of DLT at dose d_j , $p(d_j)$ is defined as (1)

$$p(d_j) = \frac{\exp(\alpha + \beta x_j)}{1 + \exp(\alpha + \beta x_j)} \quad (1)$$

where

$$x_j = \ln\left(\frac{d_j}{d^*}\right)$$

and d^* is the reference dose (in this case $d^* = 300$ mg).

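### Appendix 18 does not support the claim of good and reliable MTD selection: it gives no correct-selection or no-MTD rates, and Scenario 6, recomputed, ends without an MTD in about 42% of trials

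*Combined protocol and SAP*

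**What the plan says.** Section 3.1.2.3 summarises the simulations as showing "overall good performances in selecting the correct MTD" with about 15 evaluable patients, while limiting overdose. Appendix 18, under Simulation Results, concludes that "the design is able to provide a reliable estimate of the MTD" and that the design is fairly conservative. Section 6.1 points to Appendix 18 for the modelling and simulation behind the 9–15 evaluable patients.

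The evidence is Appendix 18, Table 2, based on 1000 trials per scenario. It gives medians with 10th and 90th percentiles for total patients, patients treated above target, DLT proportion and selected dose. A selected dose of 0 means that no MTD was found. That outcome is discussed only for the two most toxic scenarios.

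The body and the appendix also describe different designs. Section 3.1.2.3 has a "targeted toxicity interval of 25%–35" per cent and gives, as an example stopping rule, a probability above 40% of lying in it. Appendix 18 uses 20%–35% and a probability above 50%.

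**The concern.** A median inside the target range does not show how often a correct dose is selected. Table 2 gives no rate for selection in target, above target or below target, and none for finding no dose, so the reader cannot check the claim.

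The table itself gives cause for doubt. A 10th percentile of 0 means that about 10% or more of trials ended with no MTD. This holds even in Scenarios 4 and 5, whose target ranges (350–700 and 500–1000 mg) start well above the 200 mg starting dose. In Scenario 6 the 10th percentile is 0 and the median is 200, so the printed row only places the no-MTD share between about 10% and 50%. What is at stake is whether about 15 patients can be presented as enough to find the MTD reliably.

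**Working it through.** **Inputs.** From Section 3.1.2.3 and Appendix 18:
- two-parameter logistic model in ln(d/300), the "normalized dose using the reference dose" being 300 mg
- bivariate normal prior with mean (−0.797, 0.995), variances 1.699 and 1.076, covariance 0.280
- a dose grid that "starts from 200 mg and ends at 800 mg, with an increment of 50 mg", starting at 200 mg, with increments of at most 150 mg
- cohorts of 3, at most 15 patients
- a dose is admissible if P(DLT rate > 0.35) < 0.35; the next dose maximises P(target) among admissible doses, and with none admissible the trial stops with no MTD
- early stop with at least 6 patients near the MTD and P(target) > 50%; the appendix's rule for a safe maximum dose is also applied.

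**Scenario 6 truth.** Appendix 18 takes the toxicity in the prior as true. On the prior-mean curve, d = 300·exp[(logit p + 0.797)/0.995]:
- p = 0.20: 300·exp(−0.5923) = 165.9 mg
- p = 0.35: 300·exp(0.1789) = 358.8 mg.

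This reproduces the printed 166–359 mg. True DLT rates at 200, 250, 300 and 350 mg are 23.1%, 27.3%, 31.1% and 34.4%. All four lie in 20%–35%.

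**Reproducing the printed row.** Every trial path was enumerated, with the posterior by numerical integration.

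| Scenario 6, median (10th, 90th) | Printed | Recomputed |
|---|---|---|
| Total patients | 15 (3, 15) | 15 (3, 15) |
| Above target | 0 (0, 6) | 0 (0, 6) |
| DLT proportion | 33.3% (20%, 66.7%) | 33.3% (20%, 66.7%) |
| Selected MTD | 200 (0, 400) | 250 (0, 400) |

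The one difference is the median MTD. The recomputed P(selected ≤ 200 mg) is 48.9%, so a median of 200 in 1000 trials has a chance of about 25%.

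**Early stops by hand**, with p = 0.2314 at 200 mg:
- 2 or 3 DLTs of 3 in cohort 1: 3p²(1−p) + p³ = 13.6%. The appendix's decision table halts here.
- 1 of 3, stay at 200 mg, then at least one more DLT in 3: 3p(1−p)² × [1 − (1−p)³] = 0.410 × 0.546 = 22.4%. With 2/6 at 200 mg, P(DLT rate > 0.35) = 0.351, just over the cap, so the trial stops although the observed rate of 33% is inside the target.
- 0 of 3, then 3 of 3 at 350 mg: 0.454 × 0.3444³ = 1.9%. The decision table halts here too.

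Sum: 13.6 + 22.4 + 1.9 ≈ 37.8% (before rounding) stop with no MTD within six patients. Later stops add 4.5 to 5.5 points.

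**Results for Scenario 6.** Ranges reflect numerical resolution, because some dose choices are near-ties.

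| Rules | No MTD | In own target | Above target |
|---|---|---|---|
| Appendix: 20%–35%, threshold 50% | 42.4%–43.3% | 44.7%–46.5% (200–350 mg) | 11.0%–12.6% |
| Body: 25%–35%, threshold 40% | 42.3%–42.6% | 33.1%–34.4% (250–350 mg) | 17.3%–18.3% |
| Appendix, cap 0.352 | 35.1%–36.1% | about 52% | about 12% |

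Under the body's target the lower limit is 300·exp[(logit 0.25 + 0.797)/0.995] = 221.6 mg, so 200 mg is below target.

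**Sensitivity.** Adding Monte Carlo error to the posterior probabilities (SD 0.005–0.02), as a sampling-based implementation would, gives 40%–46% with no MTD. At SD 0.02 the printed median of 200 mg is also reproduced, with 46%. A cap of 0.352 gives a median DLT proportion of 26.7% rather than the printed 33.3%. A cap of 0.34 gives about 60% with no MTD and a median MTD of 0. Neither fits the printed row.

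**The case against.** The strongest reply has four parts.

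First, no document prints 42%, and the match is incomplete. Only 8 or 9 of the 12 rows of the decision table are reproduced, depending on a near-tie; the rest differ by 50 mg and lie at 350 mg or above. The sponsor's code therefore differs somewhere. This stands as a reason to give a range. It does not remove the result, because all four 200 mg rows match and most no-MTD stops occur at 200 mg.

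Second, the figure sits close to a threshold: 0.351 against 0.35, from a prior printed to three decimals. This also stands. The relaxed case still leaves more than a third of trials with no MTD and fits the printed row less well.

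Third, the appendix does print the zero percentiles and calls the design conservative, and "good" has no stated benchmark. That is fair, and no printed figure is shown to be miscalculated. The fault is a conclusion reported without the rates that would support it.

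Fourth, the algorithm does not bind. Section 3.1.2.3 lets clinical judgment override it, Section 3.1.2.2 allows up to 3 extra patients per cohort and a repeat cohort, and body Table 2 prints ≤200 where the appendix prints <200 and a halt. A reader might infer that the no-MTD rate decides whether the expansion phase can take place. The documents do not support that, since the RP2D also draws on all safety data.

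A reader might also extend the result to the other scenarios. Only their target ranges can be read. A logistic curve through the ends of the Scenario 5 range gives about 7% with no MTD, which conflicts with the printed 10th percentile of 0. Recomputed rates for those scenarios are therefore not relied on.

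**Conclusion.** The concern holds as a reporting and wording fault. The statements of good and reliable selection are not supported by what Appendix 18 reports, and Scenario 6 points the other way. With four grid doses in the appendix's target, the algorithm finds no MTD in about 42% of trials (about 40%–46% for implementations matching the printed row) and selects an in-target dose in about 45%–46%. Under the body's rules the corresponding figures are about 42% and 33%–34%.

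This rests on the prior-mean curve as Scenario 6 truth, which the printed 166–359 mg confirms, on cohorts of exactly 3, and on the algorithm being followed without clinical override. It does not show that the trial would fail to reach an RP2D.

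**What to change.** 1. Reconcile the target interval (25%–35% or 20%–35%) and the stopping threshold (40% or 50%) between Section 3.1.2.3 and Appendix 18. The review takes no position on which is right.
2. In Appendix 18, report for each scenario the percentage of simulated trials selecting a dose in target, above target and below target, and the percentage finding no MTD.
3. Replace the two summary statements, and the support that Section 6.1 draws from Appendix 18, with those figures. State that they describe the algorithm before any clinical-judgment override.

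If the appendix rules are kept, this is a re-tabulation of runs already made. If the body's rules are kept, the simulations must be rerun. Either way, at least for Scenario 6, the stated performance is likely to look less favourable.
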